12. STATISTICAL CONSIDERATIONS

12a. Sample Size Considerations

For the Aim 2 RCT, we based our sample size and power calculations on the primary outcome of retention in care, obtained from EMR data. This outcome is binary on the individual level. We used the methods described by Hussey and Hughes [32] to determine power assuming an evaluation with 24 clusters and 5 time points (including baseline). We include 24 clinics in this study to account for the possibility that 15% drop-out without replacement. We assumed that only a small proportion of the 40 HIV-positive adolescents enrolled in HIV care per clinic may be newly enrolled or recently re-engaged in care. As such, we estimated the minimum number of records per clinic for 80% power to detect a 15% difference between control and intervention periods. We assumed a coefficient of variation (τ/μ) of 0.25 and calculated the power for a two-tailed test with α =0.05. Based on relevant published data [7], we assumed that 75% of adolescents in the control period will return to clinic after first visit. Under these assumptions, we estimate needing at least 5 adolescents per clinic. As such, the lower bound of the sample size required is estimated to be 720 clinic records (6 records/site X 24 sites X 5time points). If N=20

clinics are retained, we would need 7 adolescents per site, per time point, or a minimum of 700 records total.

In the optimal scenario with an average of 40 adolescents in care at each facility, our estimated analysis sample size would be at least 4,800 (5 time points). Under the same assumptions described above, we would have >99% power to detect a 15% difference in retention between the intervention and control periods.

We expect to have adequate power to detect an intervention effect for the analysis with a broader definition of retention in care (return for any follow-up visit within 6 months), because this is likely a more common pattern of follow-up than either return among newly enrolled or return after re-engagement in care.

12b. Planned interim analyses (if applicable)

Because this is a randomized trial with a stepped-wedge (staggered roll-out) design, there will be no interim analyses or stopping rules.

12c. Overview of analysis plan

Pilot phase

Qualitative feedback from participants, actors, and faculty experts will be used to finalize the case scripts, actor checklist, and HCW satisfaction survey.

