A CONSORT diagram, adapted for a stepped-wedge design [34] will be used to show the number of HCW-participants within clusters and flow of randomized stepped wedge clusters though the five time periods. We will report the number of clinics selected for inclusion, assignment to intervention or control at each time period, and the number of HCWs trained at each facility. We will report number of excluded clusters and any reasons for exclusion. No replacement will be used. Facility-specific information – adolescent patient volume, number of HCWs and presence of any adolescent-specific service (peer groups, clinics etc.) prior to the intervention – will be grouped by clinic and recorded. Baseline values of primary and process outcomes, and socio-demographic characteristics of adolescents and HCWs will be presented in a descriptive table.

We will use generalized linear mixed models (GLMM), which are more efficient than paired ttests and linear mixed models (LMMs) in the analysis of cluster RCTs when the size of clusters is unequal [32] to compare the probability of an adolescent returning to clinic after enrollment visit OR second visit after >3 months LTFU between the intervention and control periods [35]. To estimate the effect of the intervention (*Xij*) on the individual level, we will use a GLMM model with a Poisson distribution and robust standard errors, allowing for random effects for clusters (*ui*) and fixed effects for time (*j*). This approach models individual level outcomes, adjusts for temporal trends and accounts for correlation of outcomes within a cluster (clinic). We will estimate adjusted risk ratios (ARR), adjusted risk differences (ARDs) and 95% confidence intervals at the 5% significance level (two-sided). Adjusted risk ratios will be estimated for secondary outcomes: initiating and adherent to ART (≥80% in the dosing period by pharmacy records), 12-month retention in care; viral suppression (<100 copies/ml, <1000 copies/ml), and referred for ancillary services (family planning and TB screening). Models will be adjusted for facility type, patient volume, and exposure to prior adolescent health interventions (c).

The equation for a generic model is: $Y_{ijk} = \beta_0 + \beta j_{time} + \beta_{effect} X_{ij} + \beta c X ij$, $ui + \varepsilon ij$

- Analyses of process outcomes to understand intervention mechanisms will include:
 - Mean HCW competency (passing score proportion per clinic) before and after the intervention

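### The 720- and 700-record minima for 80% power do not carry over to a Poisson mixed model with dispersion fixed at 1; how far they fall short depends on covariates, group size and clinic variation

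*Combined protocol and SAP*

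**What the plan says.** Section 12a treats retention as binary for each adolescent and uses the Hussey-Hughes method "to determine power assuming an evaluation with 24 clusters and 5 time points (including baseline"). Its assumptions are 75% return in control periods, a 15% difference, a CV of 0.25 and a two-sided 5% test. It concludes that "the lower bound of the sample size required is estimated to be 720 clinic records" (6 per site, 24 sites, 5 time points). For a trial reduced to 20 clinics, "we would need 7 adolescents per site, per time point, or a minimum of 700 records total". These minima are set for the case where "only a small proportion of the 40 HIV-positive adolescents enrolled in HIV care per clinic may be newly enrolled or recently re-engaged in care". With 40 records per clinic, "we would have >99% power to detect a 15% difference in retention between the intervention and control periods".

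Section 12c gives the primary analysis. It compares "the probability of an adolescent returning to clinic after enrollment visit OR second visit after >3 months LTFU" between intervention and control periods, and "we will use a GLMM model with a Poisson distribution and robust standard errors", with a random clinic effect and fixed time effects. It adds: "We will estimate adjusted risk ratios (ARR), adjusted risk differences (ARDs) and 95% confidence intervals at the 5% significance level (two-sided"). The models also adjust for three clinic characteristics: kind of facility, number of patients, and earlier adolescent programmes. The generic equation has an error term. The text does not say that a dispersion parameter is estimated, and it names no small-sample reference for the robust test.

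**The concern.** The power calculation and the analysis rest on different variances. Hussey-Hughes uses the binomial variance of a yes/no outcome. A Poisson likelihood with dispersion fixed at 1 takes the variance as equal to the mean: 0.75–0.90 here, against a binomial variance of 0.19–0.09. Real differences between clinics then look like ordinary Poisson noise, and the random clinic effect is estimated as zero or far too small. The treatment estimate gives too much weight to noisy comparisons between clinics and too little to changes within a clinic. Robust standard errors correct the stated uncertainty but do not recover the lost precision.

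The stated minimum is the yardstick by which the trial, or a 20-clinic remainder, would be called adequately powered. If it does not hold for the model actually used, a true 15-point gain could be missed more often than the plan says.

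**Working it through.** **1. Reproduce the plan's figures.** Inputs from section 12a: control rate 0.75, intervention rate 0.90 (15% read as an absolute difference), τ = 0.25 × 0.75 = 0.1875, so τ² = 0.03516. From section 8: 4 waves, T = 5 periods. Assumed: pooled rate 0.825, and 5 clinics per wave when 20 remain. With n records per clinic per period, σ² = 0.825 × 0.175 / n = 0.144375 / n.

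Var = Iσ²(σ² + Tτ²) / [(IU − W)σ² + (U² + ITU − TW − IV)τ²]

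- 24 clinics: U = 60, W = 1080, V = 180, so IU − W = 360 and the τ² multiplier is 3600 + 7200 − 5400 − 4320 = 1080. At n = 6, σ² = 0.02406 and Var = 0.11541 / 46.631 = 0.002475, SE 0.04975. Power = Φ(0.15/0.04975 − 1.96) = Φ(1.055) = 85.4%. At n = 5 it is 79.1%.
- 20 clinics: U = 50, W = 750, V = 150, so the multipliers are 250 and 750. At n = 7, σ² = 0.02063 and Var = 0.08102 / 31.523 = 0.002570, SE 0.05070. Power = Φ(0.999) = 84.1%. At n = 6 it is 78.6%.
- 24 × 40: above 99.9%.

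The minima of 6 and 7 records therefore follow from the plan's own method.

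**2. Why the Poisson model differs.** At the pooled rate the Poisson variance is 0.825 and the binomial variance 0.144, a ratio of 5.7. The true ratio of clinic to record variance is 0.03516 / 0.144 = 0.24. The Poisson likelihood settles near 0.015–0.019. Putting those working weights into the linear model with a sandwich variance gives power of 60.8% (24 × 6) and 60.3% (20 × 7).

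**3. Simulate the planned model without covariates.** Binary outcomes; clinic rates with mean 0.75 and SD 0.1875; no time trend and equal group sizes (both assumed). Poisson random intercept by adaptive quadrature, clinic-level sandwich, 4,000 trials per setting. Here z is the uncorrected robust test, and t uses a G/(G−1) factor with t(G−2), where G is the number of clinics.

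| Clinic rates and shift to 0.90 | 24 × 6, z / t | 20 × 7, z / t |
|---|---|---|
| Beta, logit shift | 67.5 / 61.1% | 64.6 / 57.1% |
| Beta, additive shift | 66.8 / 60.2% | 64.6 / 58.6% |
| Logit-normal | 67.8 / 61.4% | 66.1 / 57.7% |

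Under the logit-shift alternatives the clinic variance was estimated at zero in 58–72% of trials. Smaller runs of 1,000 trials with other rate shapes gave 64–71% on z. Normal rates cut at 1 gave lower power (48–50% on z), but cutting shrinks the true difference to 12 points and lowers every model. Most runs put the type I error on z at 7–8% (7.5% at 24 × 6, 8.2% at 20 × 7), with a full span of 5.5% to about 10%. On t it was 5.8% in both settings.

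**4. Add clinic-level covariates.** One binary clinic covariate explaining an assumed 30% of clinic variance gives 75–78% (z) or 70–71% (t) at 24 × 6. At an assumed 50% it gives 80–84% or 75–79%. At 20 × 7 and 50%, it gives 79% or 72%.

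**5. Where the shortfall stops (beta rates, no covariates).**
- By CV (24 × 6; 20 × 7, each z / t): 0.20: 77.6 / 72.8; 72.7 / 65.6. 0.15: 86.2 / 82.6; 84.1 / 78.2. 0.10: 93.0 / 90.8; 92.5 / 88.0.
- Records per clinic per period for 80%: on z, 10 with 24 clinics (80.8%) and 12 with 20 (81.4%), or 1,200 records each. On t, 12 (82.1%) and 14 (80.7%), or 1,440 and 1,400. The smaller runs put it at about 9 and 11.
- At 24 × 40, power is 99.8%.

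**6. Alternatives at the same minima (t reference, no covariates).** Poisson mixed model with estimated dispersion: power 83–88%, size 4.5–5.1%. Exchangeable log-link GEE with Kauermann-Carroll correction: 82–88%, 4.2–4.9%. Logistic mixed model: 87–90%, 3.8–4.3%. The log link is therefore not the cause; the fixed dispersion is.

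**The case against.** The strongest objection is that section 12c does not plan an unadjusted model. All its covariates are clinic-level, so they act on the very variance that causes the loss. This stands. The 57–68% span is the end of a range at which covariates explain nothing, and it also mixes two test references. The documents do not say how much the covariates explain.

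Second, fixed dispersion is an inference, because no software or fitting method is named and the equation has an error term. That is fair, but fixed dispersion is the ordinary meaning of a Poisson mixed model, and nothing in the text says otherwise. If estimation is intended, one sentence settles the point.

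Third, 720 and 700 are lower bounds, and Table 2 plans a complete record audit, so the real group may be larger. Six records are 8% of the 73 at the median clinic (section 5f) or 15% of the 40 at the eligibility floor (section 5c). Ten to 14 records are 14–19% or 25–35%. Waves are about nine months apart, so the group could fall on either side. Section 12a nevertheless sets these minima for exactly the small-group case.

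A reader might infer that the minimum is half of what is needed. That follows only on the t reference (720 of 1,440), which the plan does not name. On robust z it is about 60% (720 of 1,200), before covariates.

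**Conclusion.** The stated minima hold for Hussey-Hughes but are not shown to hold for the planned model. With dispersion fixed at 1, CV 0.25, 75% versus 90% and no covariates, power is about 65–68% on robust z and about 57–62% on the t reference. With covariates explaining an assumed 30–50% of clinic variance, it is about 75–84% or 70–79% at 24 × 6. The shortfall therefore ranges from large to small or absent, and the documents do not settle which. The unnamed small-sample reference is a separate gap: the uncorrected z test runs at about 7–8%, so part of its power comes from a liberal test.

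The shortfall needs fewer than about 10–14 qualifying records per clinic per period together with a CV near 0.15–0.25; at 0.15 it appears only with 20 clinics on t. A reader might conclude that the whole trial is underpowered, or that the claim of more than 99% power is wrong. Neither follows: there is no shortfall at 40 records per clinic or at CV 0.10, and none is claimed for the currently enrolled definition. All results assume equal group sizes and no time trend.

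**What to change.** Choose one, before the outcome analysis:

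1. Preferred: keep the log link and state that dispersion is estimated. One form is an exchangeable log-link GEE with a Kauermann-Carroll corrected sandwich and t(clinics minus 2), with the risk difference by standardisation. The cost is that a marginal model replaces the named mixed model.
2. Use a logistic mixed model with the same clinic and period terms, and obtain the risk ratio and risk difference by standardisation. Test by permuting the waves within the stratified scheme of section 5f, not by the model-based t-test. Under an assumed clinic autocorrelation of 0.8, the size of that t-test is 5.5% at both minima but about 21% at 24 × 40, where the corrected GEE stays at 4.0%. The permutation test itself was not simulated here.
3. Keep the fixed-dispersion Poisson model, name the small-sample reference, and restate the minimum before covariates. On robust z this is about 10 records per clinic per period with 24 clinics and 12 with 20 (about 1,200 records each). On t it is about 12 and 14 (1,440 and 1,400). This costs nothing if the group proves larger.

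In every case, report the number of newly enrolled or re-engaged adolescents per clinic from the baseline record extraction in section 11, which needs no outcome comparison. The whole change is wording and standard software, with no new data.

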2. OBJECTIVES

2a. Study Objective

This study aims to develop and evaluate a clinical training intervention utilizing standardized patient actors to improve communication and interpersonal skills of health care workers in caring for HIV infected adolescents (ages 10-24 years), resulting in increased engagement in HIV care.

2b. Specific Aims

Aim 1: To develop patient case scripts specific to adolescent HIV-related care and counseling needs in Kenya, and to establish the number of training interactions necessary to reach competency

Hypothesis: Utilization of real-world adolescent experiences in a simulated patient actor training

program will improve health care provider communication and counseling skills with adolescents in Kenyan HIV care programs

Approach: Case scripts will be developed for male and female SP actors, derived from in-depth interviews with HIV-infected adolescents. We will establish competency scores and pass/fail cut-offs with a pilot sample of 10 health care workers (HCWs).

Aim 2: To assess the impact of SP encounters on the likelihood of adolescent patients retained in HIV care, and adherent to ART at public HIV treatment facilities in Kenya

Hypothesis: SP encounters will increase provider confidence and capacity to facilitate HIV status disclosure and provide supportive interactions with HIV-infected youth, which will significantly increase retention in HIV care and improve ART adherence among adolescents.

Approach: We will utilize a stepped wedge study design to assess retention in HIV services among HIV-infected adolescents. We will compare periods when clinics have received the SP training ('exposed periods') to 'control periods' prior to this training, when clinics are providing standard care. Data will be extracted via electronic medical records.

Aim 3: To estimate the cost-effectiveness of SP training per additional adolescent retained in care and cost-utility per life-year saved and per disability-adjusted life-year (DALY) averted for each adolescent

Hypothesis: An interactive SP training program will be cost-effective

Approach: We will measure detailed healthcare and program costs. We will use these costs to (1) estimate the short-term cost-effectiveness (measured as cost per additional adolescent retained in care) and (2), use modeling methods to estimate the long-term cost utility (measured as cost per disability-adjusted life-year averted).

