HCW satisfaction	Mean HCW score per clinic	HCW survey
Adolescent patient satisfaction	Mean adolescent score per clinic	Tablet-based questionnaire
Clinical/Exploratory Outcomes		
Adherence	Refills within 1 week of scheduled return visit	Clinic/pharmacy records
Viral suppression	Viral load (VL) <1000 copies per ml and a second analysis using VL <400 copies/ml	Clinic records
Linkage to APS services	STI/TB screening, Contraception uptake, mental health referral	Clinic records
AIDS defining illness	Diagnosis of at least one AIDS defining illness per national guidelines	Clinic record
Mortality	Death during follow up	Clinic records

Aim 3: Cost Effectiveness Analysis (CEA) and Cost Utility Analysis (CUA)

This aim will assess the following measures:

- SPEED intervention costs
- Cost per additional HIV-infected adolescent retained in care
- Cost per additional life year saved and disability-adjusted life year (DALY) averted. This estimate is the gold standard in health economics. This analysis will be performed once an adequate mathematical model of adolescent DALYs is developed.

Additional exploratory outcomes

- Cost per additional HIV-infected adolescent with ≥80% adherence
- Cost per additional HIV-infected adolescent virally suppressed
- Cost per additional HIV-infected adolescent linked to APS services

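### Viral suppression has no stated denominator and is recorded mainly in adolescents who return and are tested, so its risk ratio can understate or reverse the training's effect

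*Combined protocol and SAP*

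**What the plan says.** Section 2b sets Aim 2 as the effect of the training on the "likelihood of adolescent patients retained in HIV care, and adherent to ART", with the hypothesis that retention will rise. Section 3a makes return the primary outcome and says whose return is counted: adolescents with an enrolment visit, those who re-engage after loss, and those already active in care.

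The clinical outcomes are defined less fully. Table 1 in section 3b gives viral suppression as "Viral load (VL) <1000 copies per ml", with a second cut-off, taken from clinic records. AIDS-defining illness is "Diagnosis of at least one AIDS defining illness per national guidelines", also from the clinic record, as is linkage to other services. Section 11 confirms that the source is the electronic record extract.

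Section 12c then says "Adjusted risk ratios will be estimated for secondary outcomes: initiating and adherent to ART", and continues with 12-month retention, viral suppression and referral. AIDS-defining illness and death are not in that list.

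For suppression, no section states who is in the denominator, the window in which a viral load must fall, or what happens to a client with no result. The intention-to-treat statement in 12c assigns exposure by clinic and period; it does not say who is counted in a clinical outcome. The sensitivity analyses in 12c cover calendar-time changes, lag and waning, not selective observation.

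**The concern.** A viral load enters the record only if the adolescent attends and is tested. Without a rule, a client with no result has no outcome value and drops out of the model. The suppression comparison is then restricted to clients selected by return, which is what the training is meant to change.

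Section 1a links loss from care to uncontrolled viral load and poor outcomes. Adolescents who return only because of the training may therefore be less often suppressed than those who would have returned anyway. They would be present in exposed periods and unseen in control periods. The trial could report better retention with flat or lower suppression while more adolescents are in fact suppressed in care. The 12c analysis relating satisfaction scores to suppression uses the same undefined outcome.

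Referral and recorded AIDS-defining illness share the problem to a lesser extent.

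**Working it through.** **The plan's own figures.** The documents give none for suppression. The return rates come from section 12a, which "assumed that 75% of adolescents in the control period will return to clinic after first visit" and seeks "80% power to detect a 15% difference between control and intervention periods". To see whether 15% is absolute, I reproduced the sample size by the Hussey–Hughes method. Two further inputs are from 12a: "We assumed a coefficient of variation (τ/μ) of 0.25" and "calculated the power for a two-tailed test with α =0.05".

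- τ = 0.25 × 0.75 = 0.1875, so τ² = 0.0352. With 75% v 90%, the mean proportion is 0.825 and σ² = 0.825 × 0.175 = 0.1444.
- Power is 79.1% with 5 records per clinic and period, and 85.4% with 6 (24 clinics). With 20 clinics and 7 records it is 84.1%. With 40 records it exceeds 99%.
- This matches 12a's totals of 6 × 24 × 5 = 720 and 7 × 20 × 5 = 700. A relative 15% would need about 11 and 13 records per clinic. The absolute reading, 75% to 90%, is therefore the one 12a used.

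**Suppression model.** Let a be suppression in those who return with or without training, and b suppression in those who return only because of it. Neither is in the documents; both are assumed. Assume also that training does not change a, and that everyone who returns is tested.

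- Share of those seen under training who would otherwise be unseen: 15/90 = 1/6.
- Tested-only: control a; exposed (0.75a + 0.15b)/0.90. RR = 1 − (1/6)(1 − b/a).
- Suppressed in care, over all index clients (everyone whose return is being assessed): control 0.75a; exposed 0.75a + 0.15b. RR = 1 + 0.2(b/a).

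| Case | Tested-only | All index clients |
|---|---|---|
| a = 80%, b = 50% | 80% to 75%, RR 0.94 | 60% to 67.5%, RR 1.13 |
| a from 70% to 90%, b from 30% to 60% | RR 0.89 to 0.98 | RR 1.07 to 1.17 |

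**Where the distortion shrinks or vanishes.**

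- If b = a, the tested-only RR is 1.
- If suppression in those who return anyway also rises, the dilution is cancelled at a gain of 0.2(a − b) = 0.2 × 0.30 = 6 points. Check: (0.75 × 0.86 + 0.15 × 0.50)/0.90 = 0.80.
- Section 12a expects new or re-engaged clients to be a small part of the 40 per clinic. Assume 6 of 40 move from 75% to 90% and the other 34 stay at 90%. Those seen go from 4.5 + 30.6 = 35.1 to 36.0. Tested-only suppression is (35.1 × 0.80 + 0.9 × 0.50)/36.0 = 79.25%, RR 0.99.

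**Recorded illness.** Assume 5% in those who return anyway and 15% in the rest, with training cutting it to 10% in the newly retained. True illness falls from 0.75 × 5% + 0.25 × 15% = 7.5% to 0.75 × 5% + 0.15 × 10% + 0.10 × 15% = 6.75%. Recorded illness among those seen rises from 5.0% to 5.25/90 = 5.8% (RR 1.17).

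**The case against.** The strongest reply is that the plan has chosen no biased denominator; it is silent. Table 2 specifies a complete record audit, so an all-client denominator is available and nothing excludes it. That is right, and the defect is an unspecified denominator. But silence leaves the tested-only analysis as the default, because a missing viral load cannot enter the model without a rule.

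Several stronger readings are tempting but not supported:

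- *That every clinical outcome is seen only in those who return.* Section 3a allows for deaths and transfers on record without a return, a viral load could be taken at the index visit, and a missed return can already score as a missed refill. Adherence is among the least affected outcomes.
- *That 12c plans a risk ratio for illness and death.* It does not; they appear only in Table 1.
- *That suppression must come out with the wrong sign.* The sign in the table follows from assuming b below a and no gain in those who return anyway, although Aim 2 hypothesises better adherence.
- *That the cost per additional suppressed adolescent (section 3b) would take the wrong sign.* Read as a count, suppressed adolescents rise from 60 to 67.5 per 100 in the example. The sign fails only if a tested-only proportion is used, which no section says.

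It is also fair that the all-client figure has its own bias. It rises with return and testing coverage alone. If the newly retained would have been equally suppressed in care elsewhere, the RR of 1.13 is itself an artefact. That argues against using it as the sole definition and for reporting both.

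**Conclusion.** The concern holds for viral suppression, and less strongly for referral and recorded AIDS-defining illness. As written, the plan permits a suppression risk ratio among tested clients that is conditioned on the primary outcome and can understate or reverse the effect. With 12a's 75% to 90% return and assumed suppression of 80% and 50%, the tested-only RR is 0.94 against 1.13 over all index clients. It is about 0.99 if only 6 of 40 clients shift, and 1 if the newly retained are equally suppressed or the others gain 6 points. The size is therefore uncertain; the missing specification is not. These outcomes are secondary or exploratory, and the retention result is unaffected. This is a cheap and worthwhile improvement, not a flaw in the trial's main conclusion.

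**What to change.** In sections 3b and 12c:

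- Define the suppression denominator as all index clients in the period who are on ART at the index visit. State a viral-load window, and treat recorded transfers as section 3a does, that is, not as lost.
- Report being in care with a viral load below 1000 copies/ml over that denominator, alongside suppression among tested clients. Always show the proportion tested by exposure status.
- Add a sensitivity analysis for untested clients, using bounds or inverse-probability weighting.
- Report AIDS-defining illness with the share of clients observed in exposed and control periods.
- Base the cost per additional suppressed adolescent on the count suppressed among all index clients.

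The cost is plan wording and some derived variables from the existing extract; no new data are collected. The downside is that the joint outcome moves with return and testing coverage alone and counts a client tested elsewhere as not suppressed. Neither version should therefore be reported without the other.
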